22.10.4 ECG Assessments

As only qualitative ECG assessments are planned, any clinically relevant changes occurring from screening until the last trial visit will be recorded as an adverse event.

22.10.5 Physical Examination

Any clinically relevant changes occurring from screening until the last trial visit will be recorded as an adverse event.

22.11 TOLERABILITY ASSESSMENTS

Tolerability analysis will be based on the number and percent of subjects who failed to reach the [REDACTED] due to adverse events and overall discontinuation rate. The time to withdrawal due to adverse events and overall discontinuation rate, starting from the day of study IP administration will be presented using Kaplan-Meier curves.

A similar analysis approach will be repeated for the study Part 2 duration.

22.12 EVALUATION OF PRELIMINARY EFFICACY

The below listed endpoints will be used to evaluate the preliminary efficacy of OpRegen® treatment. Descriptive statistics will be used to assess the changes in these parameters and an attempt to assess potential dose response relationships in these metrics will be done.

22.12.1 Efficacy Endpoints of Clinical Relevance

Preliminary efficacy assessments will utilize the below listed parameters:

- Directional change in the GA lesion area over time
- Overall change in the GA lesion area of the study eye over time using SD-OCT and FAF
- Change from baseline over time in BCVA as measured by ETDRS chart
- Change from initial assessment over time in retinal sensitivity (as assessed by microperimetry)
- Change from baseline over time in Reading Speed Test
- Change from baseline over time in Low Luminance BCVA
- Correlation assessment between quantitative metrics derived from FAF images, SD-OCT images and CFP images
- Correlation assessment between functional and structural changes
- Change over time in NEI VFQ-25 Quality of Life score
- Change over time in Functional Reading Independence (FRI) Index score

[REDACTED]

[REDACTED]

[REDACTED]

[REDACTED]

- [REDACTED]
 - [REDACTED]
 - [REDACTED]
- [REDACTED]
- [REDACTED]

22.13 HYPOTHESIS

The primary hypothesis is that there will be no dose-limiting toxicity (DLT) and that implantation of OpRegen[®] to subjects with progressive dry-form AMD with GA will be safe and well-tolerated.

For the purpose of this study DLT is defined as an SAE determined to be product-related.

A secondary null hypothesis is that there will be no difference in disease progression, as measured by retinal function and structure, between the treated and untreated regions in the treated eye and between treated and untreated eye of a subject.

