10.2 DOSE LIMITING TOXICITY (DLT) AND STOPPING RULES

Potential toxicities and safety issues associated with the surgical procedure and of the investigational product will be carefully monitored during this study.

Stopping Rules

[figure not shown]

Figure 2: Stopping Rules

Based on the toxicity scales presented in Section 21.1.7 (see Table 6 and Table 7), the stopping rules (Figure 2) are defined as follows:

- 2 subjects with Grade 3 ocular toxicity, except cataract, or
- One (1) subject with Grade 4 ocular toxicity, except cataract, or
- 2 subjects with Grade 3 systemic toxicity, or
- One (1) subject with Grade 4 systemic toxicity

Based on the ocular toxicity scale presented in Section 21.1.7 (see Table 6) the dose limiting toxicity are defined as follows:

- 2 subjects with Grade 3 ocular toxicity, related to the investigational product except cataract, or
- One (1) subject with Grade 4 ocular toxicity, related to the investigational product except cataract

In case a Grade 3-4 toxicity occurs during the dosing within a cohort, as defined above, in accordance with the stopping rule, the dosing of the next subjects will be postponed until a decision is made by the DSMB regarding the relation of the SAE to OpRegenand to the surgical procedure. If, according to the DSMB opinion, the SAE is not related to the investigational product and the implantation procedure, the dosing schedule of the next subjects will be continued according to the

study plan. In case the event is related to the investigational product and the implantation procedure (dose limiting toxicity), dose adjustment and/or surgical procedure modification will be performed in accordance with recommendations of the DSMB.

The study sponsor is ultimately responsible for all decisions.

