All SAEs (DLTs refer to section 10.2) will be carefully monitored throughout the course of the study. Collection of SAE information will begin upon the subject's signing of the informed consent through the end of the long-term follow-up period, or for as long as is necessary per the Investigator's discretion (whichever is later). SAEs may be either spontaneously reported or elicited during questioning and examination of the subject. All identified SAEs must be recorded and described in the subject's source records. If known, the diagnosis of the underlying illness or disorder should be recorded, rather than its individual symptoms. All SAEs will be classified as related or not related to the study drug. All SAEs must be reported to the Sponsor as soon as possible and no later than 24 hours after the Investigator has knowledge of the event. Serious adverse events will be reported by completing the SAE form provided by the Sponsor. Refer to the Safety Management Plan for procedures and reporting requirements.

If a subject terminates study participation early after receiving any amount of study drug/SAEs will be collected for at least 12 weeks after the last dose

of per protocol drug, regardless of the investigator's opinion of causation. Thereafter, SAEs are not required to be reported unless the investigator feels the events were related to either study drug/per protocol medication, or a protocol procedure.

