21.1.5 Event Expectation

Unexpected: An event is considered “unexpected” when its nature (specificity) or severity is not consistent with the list of potential adverse reactions included in the current Investigator’s brochure.

Expected: An event is considered “expected” when its nature and severity are consistent with the list of potential adverse reactions included in the current IB.

21.1.6 **Recording of Adverse Events**

At each contact with the subject the study Investigator or his/her designee will seek information on AEs by specific questioning and examination. Information on all AEs will be immediately recorded in the source document and the data will be transferred to the CRF. All clearly related signs, symptoms and abnormal results will be recorded in the source document. The CRF will include a description, onset and resolution date, duration, maximum severity, assessment of causality, other suspected agent, subject's preexisting disease, action taken and outcome.

All AEs occurring during the study and long-term follow up period will be recorded and graded as described in [Section 21.1.7](#). The clinical course of each event will be followed until resolution, stabilization or until it has been reported as non-related to the investigational product.

21.1.7 **Toxicity Grading**

The AEs will be graded using NCI's CTCAE.

The list of potential ocular toxicities and their grading is shown in [Table 6](#). This list is a modification of the Ocular/Visual Adverse events v.3.0 (CTCAE), considering the specific subject population and the circumstances of the intervention.

The following AEs are defined as ocular toxicity and are to be assessed for grading as follows:

Table 6. Ocular toxicity scale

Toxicity	Grade 1	Grade 2	Grade 3 SAE	Grade 4 SAE
Keratitis (corneal inflammation/cornea ulceration)	Abnormal ophthalmologic changes only; intervention not indicated	Symptomatic; Medical intervention indicated	Symptomatic; Surgical intervention indicated	Perforation or blindness (worse than baseline visual function)
Glaucoma	Elevated intraocular pressure (EIOP) warranting topical agent for intervention	EIOP requiring topical agents and oral agents for intervention	EIOP requires operative intervention	Uncontrolled EIOP, resulting in blindness (worse than baseline visual function)

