Cataract	Mild change from baseline, detected on ophthalmologic examination, not warranting intervention	Moderate change from baseline, detected on ophthalmologic examination, not warranting intervention	Severe change from baseline, detected on ophthalmologic examination, not warranting intervention NOT SAE	Severe change warranting operative intervention NOT SAE
Uveitis	Mild anterior uveitis, not warranting intervention	Moderate anterior uveitis, warranting intervention	Severe posterior or pan-uveitis, warranting medical intervention	Severe uveitis warranting operative intervention and threatening ocular integrity
Vitreous hemorrhage	Mild hemorrhage detected on ophthalmologic examination, not warranting intervention	Moderate hemorrhage not warranting intervention	Severe hemorrhage warranting vitrectomy	Uncontrolled vitreous hemorrhage, threatening ocular integrity
Retinal detachments/PVR (Proliferative vitreoretinopathy)	Localized, peripheral intervention not indicated	Not resolving; intervention not indicated	Operative intervention indicated	Operative failure, threatening ocular integrity

Systemic toxicity will be graded based on the scale, shown in [Table 7](#).

The following AEs are defined as systemic toxicity and are to be assessed for grading as follows:

Table 7. Systemic toxicity scale

Grade	Definition
1	Mild toxicity, usually transient, requiring no special treatment and generally not interfering with daily activities.
2	Moderate toxicity which may be ameliorated by simple therapeutic maneuvers, and impairs usual activities
3 SAE	Severe toxicity which requires therapeutic intervention and interrupts usual activities. Hospitalization may or may not be required.
4 SAE	Life-threatening toxicity which requires hospitalization

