21.3.4 Reporting to Regulatory Authorities

The Sponsor or his authorized representative will notify the FDA or any other relevant regulatory authorities of any unexpected, serious adverse event or fatal or life-threatening experience associated with study procedures as soon as

possible, in accordance with regulatory requirements. As per 21 CFR 312.32, unexpected fatal or life-threatening suspected adverse reactions are reported by telephone or fax no later than seven (7) calendar days after knowledge of the event. All serious, unexpected, suspected adverse reactions and Grade 3-4 ocular toxicities (except cataract) related to the investigational product, such as intraocular infection, inflammation, retinal detachment, tumor/ectopic tissue formation will be reported to the FDA via a written report within fifteen (15) days of receipt of the information.

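### Protocol 10.2 and Protocol 22.13/SAP 3.3 define dose-limiting toxicity differently, so the same events can give opposite answers on the no-DLT hypothesis and on the MTD

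*Protocol*

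**What the plan says.** Three statements about DLT stand in the current text.

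- **The list in Protocol 10.2.** It opens "Based on the ocular toxicity scale presented in Section 21.1.7 (see Table 6) the dose limiting toxicity are defined as follows". The first limb is a joint condition on a pair of participants: "2 subjects with Grade 3 ocular toxicity, related to the investigational product except cataract, or". The alternative limb needs only a single participant at the higher grade: "One (1) subject with Grade 4 ocular toxicity, related to the investigational product except cataract". Section 21.1.2 points here: "All SAEs (DLTs refer to section 10.2) will be carefully monitored throughout the course of the study".
- **The closing paragraph of Protocol 10.2.** It deals with toxicity that meets the stopping rules. Those rules count ocular and systemic events separately: two subjects at Grade 3, or one at Grade 4, for each. The paragraph puts the label dose limiting toxicity, in brackets, on such an event when it is related to the product and to the implantation procedure.
- **Protocol 22.13 and SAP 3.3.** "For the purpose of this study DLT is defined as an SAE determined to be product-related". There is no limit by body system, grade or number of subjects.

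Protocol 22.14 and SAP 7.0 then say that a dose exceeds the MTD when two or more subjects in one cohort have DLT. Tables 6 and 7 label Grades 3 and 4 as SAE, with cataract excepted. Table 7, for example, gives that label to systemic Grade 3, described as "Severe toxicity which requires therapeutic intervention and interrupts usual activities".

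**The concern.** A yes-or-no primary conclusion needs one definition of the event. Here the section headed DLT and the section that states the hypothesis disagree, and no text says which governs. A study report written from 10.2 could state that there was no DLT although a product-related SAE had occurred. A report written from 22.13 would state the opposite on the same data. The MTD conclusion has the same problem.

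The MTD rule also fits one definition and not the other. It counts subjects who have DLT. Under 22.13 each subject either has a product-related SAE or does not. The Grade 3 limb of 10.2 is met only by two subjects together, so no single subject has it. Section 10.2 also does not say whether the two must be in the same cohort.

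**Working it through.** The plan states no power, error rate or event rate for this rule, so there is no figure to reproduce. The check applies each wording to fixed event patterns.

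**Inputs.** DLT wordings: Protocol 10.2 (list and closing paragraph), 22.13, SAP 3.3. MTD rule: Protocol 22.14, SAP 7.0. SAE labels: Tables 6 and 7.

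**Rules as applied** to one cohort, with every event product-related and non-cataract, and different events in different subjects:

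- 22.13: DLT subjects = subjects with a product-related SAE. The no-DLT hypothesis fails at 1 or more; the MTD is exceeded at 2 or more.
- 10.2 list: met if Grade 3 ocular subjects ≥ 2 or Grade 4 ocular subjects ≥ 1.
- 10.2 closing paragraph: needs a stopping rule to be met (Grade 3 ocular ≥ 2, Grade 4 ocular ≥ 1, Grade 3 systemic ≥ 2, or Grade 4 systemic ≥ 1), and the event to be procedure-related as well as product-related.

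| Pattern | 22.13 / SAP 3.3 with MTD rule | 10.2 list | 10.2 closing paragraph |
|---|---|---|---|
| A. One Grade 3 ocular | 1 subject: DLT; MTD not exceeded | No DLT (1 < 2) | No DLT (1 < 2) |
| B. One Grade 3 systemic | 1 subject: DLT; MTD not exceeded | No DLT (not ocular) | No DLT (1 < 2) |
| C. One Grade 4 systemic | 1 subject: DLT; MTD not exceeded | No DLT (not ocular) | DLT only if also procedure-related |
| D. One Grade 3 ocular and one Grade 3 systemic | 2 subjects: MTD exceeded | No DLT (1 ocular < 2) | No DLT (1 ocular < 2, 1 systemic < 2) |
| E. Two Grade 3 systemic | 2 subjects: MTD exceeded | No DLT (not ocular) | DLT only if also procedure-related |
| F. One Grade 4 ocular and one Grade 3 systemic | 2 subjects: MTD exceeded | DLT in 1 subject; 1 < 2, MTD not exceeded | At most 1 subject; MTD not exceeded |
| G. Two Grade 3 ocular | 2 subjects: MTD exceeded | DLT; not stated whether this is two subjects with DLT or one joint DLT | Same question, if also procedure-related |
| H. One Grade 4 ocular | 1 subject: DLT; MTD not exceeded | DLT in 1 subject; MTD not exceeded | DLT if also procedure-related |

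**Reading the table.**

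1. A and B give opposite answers on the no-DLT hypothesis whichever part of 10.2 is used.
2. D gives opposite answers on both the hypothesis and the MTD, again on either part of 10.2.
3. F agrees that a DLT occurred (on the list) but differs on the MTD.
4. C and E depend on which part of 10.2 is followed and on procedure-relatedness.
5. G agrees on the MTD only if the joint condition is counted as two subjects.
6. H agrees between 22.13 and the 10.2 list.

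Between 22.13 and the 10.2 list the conflict runs one way. Everything on the list is a product-related SAE by the Table 6 labels, so 22.13 can find a DLT that the list does not, but not the reverse.

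**The case against.** The best defence is that the statistical text is coherent. Section 22.13 presents its definition as the one for this study, 22.14 applies it, SAP 3.3 repeats it and SAP 7.0 uses it. Section 22.1 lets the SAP modify the protocol's analysis plans. The pointer in 21.1.2 is a parenthesis about monitoring SAEs. No formal test is planned. One could add that 10.2 governs dosing decisions and 22.13 governs analysis.

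Part of this stands: an author who uses only the SAP meets one definition. But SAP 3.3 neither mentions 10.2 nor says that it replaces it. The split between dosing and analysis also fails, because 22.14 uses DLT to decide whether the next cohort may open. Figure 2, the redacted part of 10.1 and the DSMB charter could not be seen and might help, but the conflicting text would remain.

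Four stronger readings are tempting and are not supported:

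- **That 10.2 can never treat systemic events as DLT.** The list does not, but the closing paragraph can, if the event meets a stopping rule and is also procedure-related.
- **That safety oversight had a gap.** Systemic Grade 3 and 4 events count towards the stopping rules, and escalation required DSMB review.
- **That serious ocular events without a Table 6 row necessarily fall outside 10.2.** Section 21.3.4 speaks of Grade 3-4 ocular toxicities "related to the investigational product, such as intraocular infection, inflammation, retinal detachment, tumor/ectopic tissue formation", in terms close to those of 10.2, so the table need not be read as closed.
- **That the SAP's reporting conventions would hide a zero DLT count.** SAP 10.0 blanks a percentage of zero; that sentence does not blank the count.

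Nor should the share of table cells or patterns that disagree be read as a measure of size. It reflects how the tables are laid out.

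**Conclusion.** The inconsistency is real and should be fixed before database lock. Its size is best given as the fewest events that change a conclusion: one subject among 24 for the no-DLT hypothesis (patterns A and B), and two subjects in one cohort for the MTD (pattern D). In Cohorts 1 and 2 that is two of three subjects. No probability is attached, because the documents give no event rates.

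This rests on three assumptions: that the SAE labels in Tables 6 and 7 are applied as printed; that the closing paragraph of 10.2 carries over the counts in the stopping rules; and that its reference to product and procedure means both. Patterns A, B and D do not depend on the third.

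The SAP describes dosing as finished (4.0) and DSMB reviews as held (6.0). What is at stake is therefore the DLT and MTD statements in the study report. The documents do not settle which definition is right, and this review does not choose one.

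**What to change.** Before database lock:

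1. Reconcile Protocol 10.2 (both the list and the closing paragraph), 21.1.2, 22.13 and 22.14 with SAP 3.3 and 7.0. One subject-level DLT definition, chosen by the sponsor with the DSMB, should govern both the primary conclusion and the MTD rule.
2. State in the SAP and the study report that the choice was made in an open-label study after data had accumulated.
3. Add one table to SAP Section 11: number of subjects with DLT over number treated, by cohort and overall, with the MTD result for each cohort. Show the result under the other wording beside it, so that a reader can see whether the choice mattered. The SAP already plans serious-event, ocular-toxicity and systemic-toxicity outputs, but none is named as the DLT count.

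Cost: SAP wording and one table, plus a protocol amendment or a documented clarification if protocol text changes. No new data are needed.

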22.14 STATISTICAL METHODS

For the primary hypothesis the dose will be defined to exceed the maximally tolerated dose (MTD) if at least two of the subjects in a cohort have DLT.

If the dose has not exceeded the MTD in Cohort 1, the study will proceed to Cohort 2, pending the DSMB review. If the dose has not exceeded the MTD in Cohort 2, the study will proceed to Cohort 3, pending the DSMB review of data from Cohorts 1 and 2. Enrollment of Cohort 4 will proceed only after review of the accumulated safety data by the DSMB.

For the secondary hypothesis concerning changes in retinal structure and function following OpRegen[®] implantation, the small number of subjects (3 per cohort in Cohorts 1 and 2, up to 6 in Cohort 3 and approximately 12 in Cohort 4) precludes any definitive assessment of change through formal statistical testing. However, the following data analytical techniques will be used to describe the retinal structure and function results: assessing the changes in treated eyes will involve comparing the magnitude of observed changes in retinal structure and function to the distribution of changes between visits in a given subject (including historical data, when available), and will be also compared to the same measures gathered from previously studied populations of similarly affected subjects.

Measurements of retinal structure and function made on the non-treated eye of each subject will also be examined in the same way as for the treated eye to evaluate the extent to which placebo effects or unexpected temporal trends may be contributing to observed changes in retinal function. The non-treated eyes form a good comparison group for the fellow treated eyes in terms of rate of enlargement of GA.

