8.1.1 Number of Subjects

Approximately 24 subjects will be enrolled in four cohorts, with three subjects enrolled in each of the first two cohorts, up to 6 subjects in the third cohort, and approximately 12 subjects enrolled in the fourth cohort.

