#### 4.0 STUDY DESIGN

Open-label, dose escalation study of 24 subjects with advanced dry-[AMD](#) and [GA](#) divided into four cohorts ([Figure 1](#)):

##### Cohorts 1 – 3

The first 2 cohorts, consisted of 3 eyes of 3 legally blind subjects with best corrected visual acuity of 20/200 or less in the study eye, all received a single subretinal implantation of OpRegen.

The third cohort included 6 eyes of 6 subjects with best corrected visual acuity of 20/200 or less in the study eye, all received a single subretinal implantation of OpRegen.

Staggered intervals and safety data review by the independent data safety monitoring board ([DSMB](#)) occurred within and between cohorts to ensure subjects safety and welfare.

##### Cohort 4

The fourth cohort included 12 eyes from 12 subjects with [BCVA](#) between 20/64 and 20/250 in the study eye, all received a single subretinal targeted implantation of OpRegen.

Staggered intervals and safety data review by the [DSMB](#) occurred between at least the first two subjects of each delivery modality to ensure subject safety and welfare.

[figure not shown]

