## 6.4 Descriptive Statistics

All measured variables and derived parameters will be listed individually and if appropriate, presented in summary tables by dose regimen group and overall, providing sample size, absolute and relative frequency for categorical variables, or sample size, arithmetic mean, standard deviation, median, minimum, and maximum for continuous variables. [Confidence intervals](#) will be presented for the efficacy endpoints for exploratory purposes only.

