## 7.0 STATISTICAL METHODS

All data collected for this study will be presented in summary tables, listings, and figures (TLFs) as indicated in [Section 11](#) of this SAP. Shells for TLFs with enough detail for programming will be provided as a guide to develop the programming SAS codes. These shells will be in sufficient detail to simulate the actual TLFs when they are created from the locked database.

Tabulations for continuous data will use a standard set of summary statistics: number of observations available (n), mean, standard deviation ([SD](#)), median, and range (minimum, maximum).

Categorical or dichotomous data will be tabulated using counts and percentages. The numerator and denominator for each percentage calculation will be specified in the footnotes of table shells.

Data listings will present all information recorded in [eCRFs](#) and any derived variable(s) included in the analysis datasets for all subjects and visits.

For the SAP primary hypothesis, the dose will be defined to exceed the maximally tolerated dose ([MTD](#)) if at least two of the subjects in a cohort have [DLT](#).

If the dose has not exceeded the [MTD](#) in Cohort 1, the study will proceed to Cohort 2, pending the [DSMB](#) review. If the dose has not exceeded the [MTD](#) in Cohort 2, the study will proceed to Cohort 3, pending the [DSMB](#) review of data from Cohorts 1 and 2. Enrollment of Cohort 4, using either method of surgical delivery, will proceed only after review of the accumulated safety data by the [DSMB](#).

For the SAP secondary hypothesis concerning changes in retinal structure and function following OpRegen implantation, the small number of subjects (3 per cohort in Cohorts 1 and 2, up to 6 in

Cohort 3 and approximately 12 in Cohort 4) precludes any definitive assessment of change through formal statistical testing. However, the following data analytical techniques will be used to describe the retinal structure and function results: assessing the changes in treated eyes will involve comparing the magnitude of observed changes in retinal structure and function to the distribution of changes between visits in a given subject (including historical data, when available), and will be also compared to the same measures gathered from previously studied populations of similarly affected subjects.

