## 8.0 GENERAL CONSIDERATIONS

In general, numerical variables in demographic and baseline characteristics will be summarized by displaying: n (non-missing sample size), mean, standard deviation, median, quartiles, maximum and minimum. The frequency and percentages (based on the non-missing sample size) of observed

levels will be reported for all categorical measures. Percentages will be calculated out of the total number of subjects per group.

Numerical effectiveness variables described above will be summarized displaying n, mean, median, standard deviation ([SD](#)), standard error (SE), quartiles, minimum, maximum.

All summary tables will be structured with a column for either treated or fellow eye.

No inferential statistics will be applied to baseline characteristics and safety variables unless specified otherwise.

In general, all data will be listed and sorted by treatment or fellow eye status, cohort number, site and subject, and when appropriate by visit number (or assessment date) as appropriate.

Most data manipulation, tables, figures, listings, and analysis will be documented in SAS programs and performed using SAS® Software version 9.4.

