### **Statistical summary conventions**

For tables, sample sizes for each treatment group will be presented as totals in the column header (N=x), where appropriate. Sample sizes shown with summary statistics are the number (n) of subjects with non-missing values.

Summaries for categorical variables will include only categories that subjects had a response in. Percentages corresponding to null categories (cells) will be suppressed. All summaries for continuous variables will include: N, mean, and SD. Other summaries (e.g. median, quartiles, 5%, 95% intervals, CV or %CV) will be used as appropriate. All percentages should be rounded and reported to a single decimal place (xx.x%). If percentages are reported as integers, percentages greater than 0% but <1% will be reported as <1%, whereas percentages greater than 99% but <100% will be reported as >99%. A percentage of 100% will be reported as 100%. No value of 0% should be reported. Any computation of percent that results in 0% is to be reported as a blank. P-values will be reported with three decimal places with a leading zero (0.001). P-values <0.001 will be reported as <0.001.

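### The MTD label uses a fixed count of two DLTs whatever the cohort size, and the SAP plans no DLT-labelled row or interval, so a result of zero DLTs would be reported without an upper bound

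*Protocol*

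**What the plan says.** **The rule.** Protocol 22.14: "the dose will be defined to exceed the maximally tolerated dose (MTD) if at least two of the subjects in a cohort have DLT". SAP 7.0 repeats it and ties it to the primary hypothesis: "For the SAP primary hypothesis, the dose will be defined to exceed the maximally tolerated dose". Neither text varies the count with cohort size.

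**Its written use.** Protocol 22.14: "If the dose has not exceeded the MTD in Cohort 1, the study will proceed to Cohort 2, pending the DSMB review". The same wording governs the step from Cohort 2 to Cohort 3. Cohort 4 opens on DSMB review of the accumulated safety data, with no count attached.

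**Cohort sizes.** Protocol 8.1.1 plans three subjects in each of the first two cohorts, "up to 6 subjects in the third cohort, and approximately 12 subjects enrolled in the fourth cohort". SAP 4.0 reports 3, 3 and 6, and for the last: "The fourth cohort included 12 eyes from 12 subjects with" BCVA in the stated range.

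**Definition.** SAP 3.3 and Protocol 22.13 define a DLT as a product-related SAE. The primary hypothesis is that there will be none and that implantation will be safe and well tolerated.

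**Reporting.** SAP 7.1.6 plans a topline table by cohort giving events, subjects and percentage of subjects. One line covers subjects with at least one OpRegen-related TEAE or treatment-emergent SAE. On intervals, SAP 6.4 says they "will be presented for the efficacy endpoints for exploratory purposes only". SAP 8.0 says: "No inferential statistics will be applied to baseline characteristics and safety variables unless specified otherwise". SAP 10.0 says: "Any computation of percent that results in 0% is to be reported as a blank".

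**The concern.** The primary objective is safety, and the SAP attaches a yes/no statement about the MTD to it. That statement carries a different meaning in each cohort size. One DLT in six eyes is not labelled and two in twelve is, although the observed rate is the same.

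The rest of the planned output does little to put the label in context. The closest row, in SAP 7.1.6, joins non-serious and serious related events in its wording. It therefore need not equal the DLT count under SAP 3.3. Neither that topline table nor any table by relationship to OpRegen is in the SAP Section 11 list, where the only relationship table concerns the per-protocol treatment. With no DLTs the percentage would be blank. A reader would have no indication of how little zero events in 3 or 6 eyes can rule out.

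**Working it through.** **1. Inputs.** The count of two comes from Protocol 22.14 and SAP 7.0. Cohort sizes 3, 3, 6 and 12 come from SAP 4.0; they add to 24, the stated total. The documents give no target DLT rate or operating characteristic for the rule, so there is no figure of the plan's own to reproduce. True DLT rates of 5%, 10% and 20% below are assumptions.

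**2. Observed rate at the trigger.** 2/3 = 67%, 2/6 = 33%, 2/12 = 17%. Since 1/6 = 2/12 = 16.7%, equal observed rates can fall on opposite sides of the rule. The exact (Clopper-Pearson) 95% intervals overlap heavily: 0.4% to 64.1% for 1/6 and 2.1% to 48.4% for 2/12.

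**3. Chance that the rule is met.** For n eyes and true rate p:

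P(at least 2) = 1 − (1 − p)^n − n·p·(1 − p)^(n−1)

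For n = 12 and p = 0.10: 1 − 0.2824 − 0.3766 = 0.3410.

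| Assumed true rate | n = 3 | n = 6 | n = 12 |
|---|---|---|---|
| 5% | 0.7% | 3.3% | 11.8% |
| 10% | 2.8% | 11.4% | 34.1% |
| 20% | 10.4% | 34.5% | 72.5% |

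The true rate at which the rule is met half the time is 50%, 26.4% and 13.6% for n = 3, 6 and 12.

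**4. Opposite labels in Cohorts 3 and 4 (illustration only).** Write L6 and L12 for the table entries and assume equal, independent rates:

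P(opposite) = L12(1 − L6) + L6(1 − L12)

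At 10%: 0.3410 × 0.8857 + 0.1143 × 0.6590 = 0.3020 + 0.0753 = 0.3773. At 5% it is 0.1434 and at 20% it is 0.5699.

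**5. What zero DLTs would exclude.** The exact two-sided 95% upper limit for 0/n is 1 − 0.025^(1/n):

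| Result | Upper 95% limit |
|---|---|
| 0/3 | 70.8% |
| 0/6 | 45.9% |
| 0/12 | 26.5% |
| 0/24 | 14.2% |

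This step does not depend on any assumed DLT rate. It is the part the planned output would leave out.

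**6. Planned output compared with what is needed.**

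| Needed to read the DLT result | In the SAP |
|---|---|
| Subjects with a product-related SAE, by cohort | Joined with related TEAEs in one line of 7.1.6 |
| The name DLT on an output | None in the Section 11 tables, figures or listings |
| An interval | Efficacy endpoints only (6.4); none for safety unless specified (8.0) |
| A visible zero | 0% printed as a blank (10.0) |

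**The case against.** The case against has five parts.

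- **The label has little use.** Its written gates apply only to the two cohorts of three, and no listed output prints an MTD label by cohort. The 1/6 against 2/12 contrast is therefore something a reader might construct, not something the plan is scheduled to display. This stands. It removes any claim that escalation was misdirected.
- **Much of the DLT content is already planned.** Besides the topline line, SAP 7.1.6 plans a table of TEAEs by possible relationship to OpRegen. SAP Section 11 lists tables for serious TEAEs, ocular toxicity and systemic toxicity, and a listing of SAEs. A reader might infer that the SAP reports nothing on DLTs; the documents do not support that. What is missing is narrower: a separate, named row and an interval.
- **The blank is minor.** Column headers carry N where appropriate, so a reader could recover the zero. That is fair, but the upper bound would still be absent.
- **The plan is openly descriptive.** Protocol 22.1 and SAP 3.3 disclaim power and formal testing. An exact interval is also descriptive and involves no test, and SAP 8.0 leaves room for it where specified.
- **The opposite-label figures are hypothetical.** Cohort 4 has better vision (Protocol 6.1) and uses two formulations and two delivery systems (Protocol synopsis). The doses by cohort cannot be seen in the public text. Equal rates in Cohorts 3 and 4 are an assumption, and this objection stands in full.

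**Conclusion.** The point holds as a reporting improvement. The MTD label means different things at 3, 6 and 12 eyes. The plan would also report the result that its primary hypothesis predicts without a percentage or an upper limit. The limits are wide: 70.8% for 0/3 and still 14.2% for 0/24. They rest only on binomial counts, with one common rate across all 24 subjects for the last.

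Two stronger readings are not supported. First, a reader might infer that the fixed count biased dose escalation or decides the primary hypothesis. It does neither: the written gates involve equal cohorts of three, the DSMB review and the stopping rules in Protocol 10.2 stand apart from it, and any single DLT already contradicts the hypothesis of none. In the 12-eye cohort the rule errs towards caution. Second, the opposite-label chances of 14.3%, 37.7% and 57.0% might be read as forecasts. They only show how the rule behaves under equal, independent rates that the documents do not give.

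**What to change.** 1. **SAP 7.0.** Keep the prespecified label and do not set a new threshold now that the study is open-label and all cohorts are treated. Add a sentence saying that it served as an escalation gate for Cohorts 1 and 2 only and is not comparable across cohorts of different size.
2. **SAP 7.1.6.** Give OpRegen-related treatment-emergent SAEs their own row, labelled DLT. Show subjects affected over subjects treated with Clopper-Pearson 95% intervals, by cohort and overall, and by target dose where the doses match.
3. **Definition.** State in the table that DLT has the SAP 3.3 meaning. Protocol 10.2 uses the same term for two subjects with related Grade 3 ocular toxicity, or one with related Grade 4, cataract excepted.
4. **SAP 10.0.** Print 0/n with its upper limit, as a stated exception to the blank-for-zero convention.
5. **SAP Section 11.** List the table.

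The cost is one small table from SAE and relatedness data already collected, one line in the table list and a few sentences. SAP 2.0 allows revisions before database lock. Conduct, DSMB review and stopping rules do not change. The downside is that wide intervals make the safety statement look less firm.
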